Attachment 1: Eastern Cooperative Oncology Group Performance Status

Grade	ECOG Performance Status
0	Fully active, able to carry on all predisease performance without restriction
1	Restricted in physically strenuous activity but ambulatory and able to carry out work of a
	light or sedentary nature, eg, light house work, office work
2	Ambulatory and capable of all self-care but unable to carry out any work activities. Up and
	about more than 50% of waking hours
3	Capable of only limited self-care, confined to bed or chair more than 50% of waking hours
4	Completely disabled. Cannot carry on any self-care. Totally confined to bed or chair
5	Dead

109

Attachment 2: Prior Cancer Therapy for Multiple Myeloma

A line of therapy is defined as one or more cycles of a planned treatment program. This may consist of one or more planned cycles of single-agent therapy or combination therapy, as well as a sequence of treatments administered in a planned manner. For example, a planned treatment approach of induction therapy followed by autologous stem cell transplantation, followed by maintenance is considered one line of therapy. A new line of therapy starts when a planned course of therapy is modified to include other treatment agents (alone or in combination) as a result of disease progression, relapse, or toxicity. A new line of therapy also starts when a planned period of observation off therapy is interrupted by a need for additional treatment for the disease.

Source: Rajkumar 2011²¹

Attachment 3: New York Heart Association Criteria for Functional Classification

Functional Capacity	Objective Assessment
Class I. Patients with cardiac disease but without resulting limitation of physical	A. No objective evidence
activity. Ordinary physical activity does not cause undue fatigue, palpitation,	of cardiovascular disease
dyspnea, or anginal pain.	
Class II. Patients with cardiac disease resulting in slight limitation of physical	B. Objective evidence of
activity. They are comfortable at rest. Ordinary physical activity results in	minimal cardiovascular
fatigue, palpitation, dyspnea, or anginal pain.	disease
Class III. Patients with cardiac disease resulting in marked limitation of physical	C. Objective evidence of
activity. They are comfortable at rest. Less than ordinary activity causes fatigue,	moderately severe
palpitation, dyspnea, or anginal pain.	cardiovascular disease
Class IV. Patients with cardiac disease resulting in inability to carry on any	D. Objective evidence of
physical activity without discomfort. Symptoms of heart failure or the anginal	severe cardiovascular
syndrome may be present even at rest. If any physical activity is undertaken,	disease
discomfort is increased.	

The Criteria Committee of the New York Heart Association. Nomenclature and criteria for diagnosis of diseases of the heart and great vessels. 9th ed. Boston, Mass: Little, Brown, & Co; 1994:253-6.

111

Attachment 4: Conversion Table for Glucocorticoid Dose

	Oral or Intravenous
Generic Name	Dose (mg)
Dexamethasone	0.75
Hydrocortisone	20
Methylprednisolone	4
Prednisolone	5
Prednisone	5

Attachment 5: International Myeloma Working Group Uniform Response Criteria

The following criteria for response to multiple myeloma treatment were presented by Rajkumar, et al.²¹

Response	Response Criteria
Stringent complete	CR as defined below, plus
response (sCR)	Normal FLC ratio, and
	Absence of clonal PCs by immunohistochemistry or 2- to 4-color flow
	cytometry
Complete response (CR) ^a	Negative immunofixation of serum and urine, and
	Disappearance of any soft tissue plasmacytomas, and
	• < 5% PCs in bone marrow
Very good partial	Serum and urine M-component detectable by immunofixation but not on
response (VGPR) ^a	electrophoresis, or
	• ≥ 90% reduction in serum M-component plus urine M-component
	< 100 mg/24 hours
Partial response (PR)	• ≥ 50% reduction of serum M-protein and reduction in 24-hour urinary
	M-protein by $\geq 90\%$ or to $< 200 \text{ mg/}24 \text{ hours}$
	• If serum and urine M-protein are not measurable, a decrease ≥ 50% in the
	difference between involved and uninvolved FLC levels is require in place of
	the M-protein criteria
	If serum and urine M-protein are not measurable, and serum free light chain
	assay is also not measurable, $\geq 50\%$ reduction in bone marrow PCs is required
	in place of M-protein, provided baseline percentage was ≥ 30%
	• In addition to the above criteria, if present at baseline, ≥ 50% reduction in the
	size of soft tissue plasmacytomas is also required.
Minimal response (MR)	• In patients with relapsed refractory myeloma adopted from the EBMT criteria:
	• $\geq 25\%$ but $\leq 49\%$ reduction of serum M-protein and reduction in 24-hour
	urine M-protein by 50% to 89%
	• In addition to the above criteria, if present at baseline, 25% to 49% reduction
	in the size of soft tissue plasmacytomas is also required
	No increase in size or number of lytic bone lesions (development of
0.11.1	compression fracture does not exclude response)
Stable disease	Not meeting criteria for CR, VGPR, PR, or progressive disease
Progressive disease ^b	• Increase of 25% from lowest response value in any of the following:
	• Serum M-component (absolute increase must be ≥ 0.5 g/dL), and/or
	• Urine M-component (absolute increase must be $\geq 200 \text{ mg/}24 \text{ hours}$), and/or
	Only in patients without measurable serum and urine M-protein levels: the
	difference between involved and uninvolved FLC levels (absolute increase
	must be $> 10 \text{ mg/dL}$

Attachment 6: Model of Worst Toxicity

As part of the rationale for dose selection in subsequent studies, the following modeling of worst toxicity will be attempted. It is based on Model 1 in Simon, et al.^a

$$y_{ij} = Ln(d_{1ij} + d_{2ij} + a_1D_{1ij} + a_2D_{2ij}) + b_i + e_{ij},$$

where

i = 1, 2, ..., n, the number of patients

j denotes the treatment cycle number

 d_{lii} denotes the total amount of daratumumab (mg) that patient i receives in course j

 d_{2ij} denotes the total amount of lenalidomide (mg) that patient i receives in course j

 D_{lij} denotes the total amount of daratumumab (mg) that patient i has received prior to course j

 D_{2ij} denotes the total amount of lenalidomide (mg) that patient i has received prior to course j

 a_1 represents the influence of prior total dose ($a_1 = 0$ indicates no cumulative toxicity)

 a_2 represents the influence of prior total dose ($a_2 = 0$ indicates no cumulative toxicity)

 b_i is a random, normally distributed intersubject effect with mean μ_b and standard deviation σ_b

 e_{ij} is the normally distributed error term, with mean zero and standard error σ_e , reflecting the within-subject variation

The unobserved variable y_{ij} translates to the observed discrete toxicity levels by means of 3 additional parameters, $k_1 < k_2 < k_3$, which divide the line into the 4 regions representing "minimal" toxicity (usually CTCAE grades 0-1), "moderate" toxicity (usually CTCAE grade 2), DLT, and "unacceptable" toxicity.

Note that the model described above handles the case where subjects receive doses that deviate from the protocolplanned ones.

The following will be estimated from the model:

- Maximum likelihood estimates (MLEs) of the parameters a_1 , a_2 , σ_b , σ_e , k_1 , k_2 , and k_3 , which yield estimated probabilities of seeing moderate toxicity and DLT at the various dose levels
- Confidence intervals for parameters with nonzero MLE
- Graph of probabilities of CTCAE grades 2+, 3+, and 4+ toxicities, for the first course averaged over the population of patients
- Graphs of probabilities of CTCAE grades 2+, 3+, and 4+ toxicities (for the first course) for patients with b equal to MLE SD, MLE and MLE + SD.

There are no guarantees that the model will converge and it may need simplifying modifications in order to do so.

115

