3.2.3.2. Daratumumab RP2D Rationale

The RP2D has been selected based on marked M-protein reduction with an acceptable safety profile in doses up to 16 mg/kg, the highest dose of Phase 1. MTD was not reached in Phase 1. The IDMC reviewed the safety data of 2, 4, 8 and 16 mg/kg cohorts and concluded that an acceptable benefit/risk profile was observed in doses up to 16 mg/kg. The majority of the Grade 3 adverse events were neutropenia, which was attributed to lenalidomide. The daratumumab/Len/Dex combination PK-profile was similar to daratumumab alone suggesting Len/Dex does not affect the pharmacokinetic profile of daratumumab.

The rationale of PR2D is also supported by the ongoing single agent daratumumab studies. Clinical pharmacokinetic data have shown the 16 mg/kg dose to be the lowest dose that results in complete target suppression at all time points. This dose and schedule continuously suppressed NK cells throughout dosing. Additionally, the overall response rate (ORR) appeared higher for the 16-mg/kg dose compared with the 8-mg/kg dose, based on early preliminary data from Part 2 of Study GEN501 and from Study MMY2002 (both ongoing) as of a cutoff date of 24 January 2014. In Study GEN501, the ORRs (ie, partial response [PR] or greater) were 11% and 40% for the 8-mg/kg (n=28) and 16-mg/kg (n=15) dose regimens, respectively. For the Study MMY2002, the unconfirmed ORRs for the 8-mg/kg and 16-mg/kg dose regimens were similar to those observed in GEN501. In addition, VGPRs were observed for 7 of 30 subjects treated with the 16-mg/kg dose in those 2 studies. VGPR had not been observed at lower dose levels. These preliminary data support that full target saturation at the 16-mg/kg dose is needed to achieve higher and deeper response rates. In addition, the 16-mg/kg dose and schedule was shown to have an acceptable and manageable safety profile for the approximately 30 subjects for whom preliminary data were available in Studies GEN501 and MMY2002, and no additive toxicity has been observed in the Phase 1 dose escalation when comparing the safety from 16 mg/kg dose cohort with lower dose cohorts.

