11.8. Exploratory Modeling

Exploratory univariate modeling will be used to investigate preliminarily relationships between select efficacy and safety variables and possibly explanatory variables.

A model of the worst toxicity will be attempted to potentially provide a rationale for dose selection in subsequent studies. This model is included in Attachment 6.

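### The exploratory worst-toxicity model fixes one milligram of lenalidomide as equal to one milligram of daratumumab, so it may misattribute toxicity when lenalidomide is reduced

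*Protocol*

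**What the plan says.** Protocol section 11.8 announces the model: "A model of the worst toxicity will be attempted to potentially provide a rationale for dose selection in subsequent studies". Attachment 6 gives the latent score for patient i in cycle j as "Ln(d_{1ij} + d_{2ij} + a_1D_{1ij} + a_2D_{2ij}) + b_i + e_{ij". Here d1 "denotes the total amount of daratumumab (mg) that patient i receives in course j" and d2 "denotes the total amount of lenalidomide (mg) that patient i receives in course j". D1 and D2 are the amounts of each drug given before that cycle, with coefficients a1 and a2.

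The parameters to be estimated are a1, a2, two standard deviations and three cut-points, "which yield estimated probabilities of seeing moderate toxicity and DLT at the various dose levels". The planned graphs of grade 2+, 3+ and 4+ toxicity are for the first cycle only, one of them "for the first course averaged over the population of patients". Attachment 6 also says that the model copes with patients whose doses depart from plan, and that simplifications may be needed for convergence. The SAP does not mention the model.

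Section 3.2.3.2 reports, on Phase 1 safety: "The majority of the Grade 3 adverse events were neutropenia, which was attributed to lenalidomide".

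**The concern.** With one drug, a coefficient of 1 on current dose is a harmless normalisation, because rescaling the dose only shifts the cut-points. With two drugs, only one can be normalised this way and the other needs its own weight. Attachment 6 supplies none for the current cycle. Expressing lenalidomide in another unit would give a different fitted curve from the same data.

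The two drugs differ greatly in milligrams per cycle. At the Phase 2 dose the sum is mostly daratumumab, although the protocol links most Grade 3 events to lenalidomide. What is at stake is any dose rationale for later studies that rests on the fitted curve, above all where patients have had lenalidomide reduced.

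**Working it through.** Attachment 6 states no numerical result, so there is no figure of the plan's own to reproduce.

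**Inputs.** Lenalidomide is 25 mg on 21 days, or 525 mg per cycle, in every cohort (section 6.2). Daratumumab is given four times in each of Cycles 1 and 2, twice per cycle in Cycles 3 to 6 and once per cycle from Cycle 7 (section 6.1). Dose levels are 2, 4, 8 and 16 mg/kg (section 3.2.3.2). Body weight is assumed at 70 kg. The Phase 1 predose of at most 10 mg is ignored and prior-dose terms are set to zero.

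**Share of the current-cycle sum, d2/(d1 + d2).**
- 2 mg/kg, four infusions: d1 = 2 × 70 × 4 = 560; 525/1085 = 48%.
- 16 mg/kg, four infusions: d1 = 16 × 70 × 4 = 4480; 525/5005 = 10%.
- 16 mg/kg, from Cycle 7: d1 = 16 × 70 = 1120; 525/1645 = 32%.

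**Effect on the score of cutting lenalidomide from 25 to 10 mg (525 to 210 mg) at 16 mg/kg.**
- Four infusions: ln(5005/4690) = 0.065.
- From Cycle 7: ln(1645/1330) = 0.21.

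**Comparison that does not depend on the error scale.** In four-infusion cycles, doubling daratumumab from 8 to 16 mg/kg adds ln(5005/2765) = 0.593. That is 0.593/0.065, about nine times the effect of the lenalidomide cut. If lenalidomide were 10 times as toxic per milligram (an assumption), the doubling would add ln(9730/7490) = 0.26 and the cut would remove ln(9730/6580) = 0.39. The order reverses.

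**Dependence on the unit.** With weight w on lenalidomide, the first-cycle contrast from 2 to 16 mg/kg is ln[(4480 + 525w)/(560 + 525w)]. It equals 2.00, 1.53, 0.80, 0.52 and 0.14 for w = 0.1, 1, 5, 10 and 50. The documents give no value of w, so this range is assumed.

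**First-cycle simulation.** The written model, with free scale and cut-points, was fitted to 6000 simulated subjects. The assumed truth was w = 10, unit error and some daratumumab effect. Probabilities of the upper two of the four toxicity categories, at 75 kg:
- 2 mg/kg, planned lenalidomide: 0.42 fitted, 0.44 true.
- 16 mg/kg, planned lenalidomide: 0.65 fitted, 0.65 true.
- Lenalidomide without daratumumab: 0.31 fitted, 0.40 true. The rise credited to daratumumab at 16 mg/kg is thus 0.34, against a true 0.25.
- Lenalidomide cut to 10 mg at 16 mg/kg: the fitted probability falls by 0.009. The assumed truth is Φ(ln[(4800 + 10·d2)/5550] − 0.2), which goes from 0.653 at d2 = 525 to 0.507 at d2 = 210, a fall of 0.146.

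**All-cycle simulation.** This used 12 cycles on the protocol schedule, with assumed lenalidomide reductions, true w = 10, and no subject effects or prior-dose terms. In a 6000-subject fit the written model gave 0.52 against a true 0.40 at 16 mg/kg with lenalidomide 10 mg. With about 44 subjects, an estimated weight had median 8.7 (5th to 95th percentile 6.4 to 23.7).

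**The case against.** A reader might infer that the model will credit lenalidomide's background toxicity to daratumumab dose. The documents do not support that. The scale and cut-points are estimated, so a constant background can be absorbed. When toxicity was simulated as coming from lenalidomide alone, the large-sample slope went to zero and the fitted probability was 0.535 at both 2 and 16 mg/kg (true 0.540). With 16 subjects and a flat truth the model did show a mean spurious rise of 0.11. That comes from a slope that cannot be negative, and a weight on lenalidomide would not cure it.

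The listed outputs are also mostly safe. They are probabilities at the daratumumab dose levels, where the first-cycle error was at most about 0.03; a Len/Dex-alone probability is not among them. Hematologic DLTs must be judged related to daratumumab (section 6.5), which keeps much lenalidomide-attributed neutropenia out of the DLT category. No such filter is stated for the graphs by grade.

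The third objection is that a free weight cannot be estimated. In the first cycle that is right: planned lenalidomide is 525 mg for everyone, and even with 6000 simulated subjects weights of 1, 5 and 10 fitted almost equally well (negative log-likelihoods 8045.6, 8046.5 and 8047.8). It does not hold across cycles, where lenalidomide reductions and the thinning daratumumab schedule carry information.

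Finally, the 10% share applies only to four-infusion cycles, and prior lenalidomide has its own coefficient. Both points stand.

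**Conclusion.** The point holds in limited form. The equal per-milligram assumption is written into the equation and no listed parameter can correct it. Planned-dose first-cycle probabilities are little affected. Predictions at reduced lenalidomide can be materially wrong: 0.52 against 0.40 in the all-cycle simulation. This sits badly with the claim that the model handles departures from planned dose.

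The score shifts rest on 70 kg and zero prior-dose terms. The simulated errors rest on an assumed tenfold weight and assumed reductions; if the true ratio were near 1, the error would vanish. The 44 subjects fall within the 42 to 58 planned for both phases together, so that precision presumes pooling, and Phase 1 alone (42 − 30 = 12 to 58 − 30 = 28) would give less.

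Severity is minor. The model is exploratory and only to be attempted. It feeds no endpoint or escalation rule, and section 3.2.3.2 gives other grounds for the Phase 2 dose.

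**What to change.** Replace the score with y = Ln(d1 + c2·d2 + a1·D1 + a2·D2) + b + e and estimate c2 from all cycles.

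If c2 is imprecise or the fit does not converge, report the probabilities over a stated range of fixed c2 values, for example 0.1 to 50, instead of at c2 = 1 only. State that first-cycle results apply at the planned lenalidomide dose.

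Do not fall back on a daratumumab-only model to separate the drugs. Ln(d1) forces toxicity to zero when no daratumumab is given: in a similar first-cycle simulation it put lenalidomide-alone toxicity at 0.00 against a true 0.40, worse than the written model's 0.30.

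The SAP should say whether the model will be run and on which phase or phases.

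The cost is one extra parameter, possibly imprecise. The allowance in Attachment 6 for simplifying changes would not supply it, so it has to be written in.

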Attachment 7: Calculated Creatinine Clearance

Cockeroft-Gault formula:

To calculate the subject's creatinine clearance (CrCl), use the following Cockcroft-Gault formula:

$$CrCl = \frac{(140 - age [in years]) \times weight (kg)}{(72 \times serum creatinine [mg/dL])} (x 0.85 \text{ for females})$$

If the serum creatinine is obtained using the International System of Units (SI) (ie, micromol/L), use the following formula to convert SI units to conventional (mg/dL) units (Manual of Laboratory & Diagnostic Tests, 2004):

• serum creatinine (micromol/L) divided by 88.4 = serum creatinine (mg/dL).

Modification of Diet in Renal Disease (MDRD)

Chronic Kidney Disease Epidemiology Collaboration (CKD-EPI)

Alternatively, creatinine clearance may be calculated or measured according to the MDRD (Levey 2006)¹⁴ or the CKD-EPI (Levey 2009)¹⁵.

For online calculators, please go to https://www.kidney.org/professionals/KDOQI/gfr calculator.

Attachment 8: Limited Schedule of Events for Subjects Continuing Daratumumab as of Amendment 7

Protocol Amendment 7 will allow those subjects who were receiving daratumumab after the primary analysis to continue receiving study drug. All subjects have received at least 12 months of therapy with daratumumab or have discontinued. Table 3 provides a limited schedule of assessments for subjects who remain on study drug after the primary analysis.

Dosage and Administration

Daratumumab, lenalidomide, and dexamethasone will be administered according to the regimen established prior to Amendment 7.

Treatment Period

As of Amendment 7, subjects will complete their ongoing cycle of treatment and all assessments for that cycle. Subjects must then sign an updated informed consent form to continue receiving study drug. At the start of the next cycle of treatment, follow the schedule outlined in Table 3. For consistency, the cycle number will not restart. Subjects who had discontinued study drug and who were in Follow-up before Amendment 7, will complete an EOT visit and enter the Follow-up Period per Table 3.

EOT Visit

This visit must occur with 3 to 5 weeks after the last dose of study drug. Week 4 immunogenicity sampling should occur at this visit (see Table 3).

Follow-up Period

As of Amendment 7, subjects who are in Follow-up (Table 2) will complete an EOT visit and immunogenicity assessments (if not yet completed) and will enter the modified Follow-up in the Time and Events Schedule (Table 3). Follow-up with Amendment 7 will include collection of best response and new antimyeloma therapy (disease assessments should be per local institutional practice), survival information, and occurrence of new cancers every 6 months for 3 years after the last dose of study drug or termination of the study by the sponsor, whichever occurs first.

Efficacy Evaluations

Investigators should monitor and assess the subjects for response to treatment or disease progression according to local institutional practice.

Safety Evaluations

Study drug administration and SAEs (including secondary malignancies) will be collected. Pregnancy testing will continue every 4 weeks during the Treatment Period and at the EOT visit. Concomitant medications associated with SAEs will also be collected. Serious adverse event reporting should continue as described in Section 12.6.2. The SAEs should be entered in the subject file/source notes.

Source Documentation

At a minimum, the type and level of detail of source data available for a study subject should be consistent with that commonly recorded at the site as a basis for standard medical care. This should also include: subject identification and study identification; study discussion and date of updated informed consent; dates of visits; drug dispensing/return records and study drug administration information.

117

Attachment 9: Limited Schedule of Events for Subjects Continuing Daratumumab as of Amendment 8

Protocol Amendment 8 will allow those subjects who are receiving daratumumab after the final analysis to continue receiving study drug. All subjects have received at least 24 months of therapy with daratumumab, or have discontinued.

Dosage and Administration

Daratumumab, lenalidomide, and dexamethasone will be administered according to the regimen established prior to Amendment 8.

Visits will occur on a monthly schedule, assessments done need to be captured in the source notes only.

Daratumumab will be provided by the sponsor until daratumumab in combination with lenalidomide and dexamethasone has been approved for use in patients with relapsed/ refractory multiple myeloma and is commercially available in the respective countries.

Treatment Period

1. INTRODUCTION

This is an open-label, dose-escalation, multicenter, Phase 1/2 safety study of daratumumab in combination with lenalidomide and dexamethasone (Len/Dex) in the treatment of subjects with relapsed or relapsed and refractory multiple myeloma. The dose escalation portion of the study (Phase 1) will be a standard 3 + 3 design and will evaluate daratumumab, at doses from 2 mg/kg up to a maximum of 16 mg/kg, in combination with Len/Dex in 28-day treatment cycles. A recommended Phase 2 dose (RP2D) will be determined during Phase 1. The Phase 2 will open to further explore the safety and efficacy of the RP2D in approximately 30 subjects.

This document serves as the statistical analysis plan for the primary analysis, covering both Phase 1 and Phase 2 of the study. As of Amendment 7, the primary analysis will be achieved. All subjects in the study have either received at least 12 months of study drug or have discontinued. Ongoing subjects may continue treatment with study drug with a limited schedule of assessments. The study treatment of daratumumab, lenalidomide or dexamethasone is referred to as the "study drug" throughout.

